CBD will be obtained in pure form from GW Pharmaceuticals (GW Pharmaceuticals 2012). Our IND has been approved (IND 125302). CBD is currently in Phase II studies for several indications including MS neuropathic pain and spasticity, and a 1:1 ratio combined CBD and THC oral spray is approved in several countries in Europe and in Canada for MS related spasticity (GW Pharmaceuticals 2012). Preclinical toxicity data suggest a good safety margin between the clinical dose proposed and a toxic dose, and doses of up to 1500mg CBD per day in humans are reported to be well-tolerated (Zuardi et al. 2006). Adverse effects of CBD/THC combined products have been subject to greater study than CBD alone, and these include dizziness, nausea, fatigue, dry mouth, somnolence, anxiety, mood changes, transient hypotension or tachycardia, delusional ideas, disorientation, and hallucinations. Most of these effects are likely attributable to the THC present in these combinations (GW Pharmaceuticals 2012). Indeed, one review

of the safety and side-effects of CBD alone noted no adverse effects across several studies (Bergamaschi et al. 2011a). However, we will take precautions against these possible adverse effects in our CBD alone study. See “Risks” for complete safety precautions. CBD alone may produce mild sedation, but does not appear to produce subjective intoxication, marked negative effects on mood or changes in cardiovascular functioning (GW Pharmaceuticals 2012).

Study Tasks:

1. International Affective Picture System (IAPS) – (Lang et al. 1999) Participants will view standardized positive, negative and neutral pictures from the IAPS. The negative and positive images will be matched on degree of valence and arousal. We will record psychophysiological facial EMG responses during a 1s baseline recording period will precede each picture, and during the 6s presentation of each (see “Psychophysiological Measures”). An Evaluative Space Grid rating will follow each picture to collect subjective reactions (see “Subjective Measures”).

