2. Dynamic Emotion Identification Task (DEIT) – In a task created for use in our laboratory (Wardle et al. 2012a), participants will view dynamically developing facial expressions composed of 2% morphs between a neutral face and a 100% expression of an emotion presented sequentially. The emotions will be happiness, sadness, anger, fear and disgust. Participants will be instructed to respond as soon as they believe they can correctly identify the emotion expressed. In this way both sensitivity (% of emotion expressed at time of identification) can be measured. Accuracy is usually near ceiling with this paradigm, and thus is not a primary dependent variable. EMG measurements will also be taken while participants view the facial expressions to examine psychophysiological reactions to the expressions (see “Psychophysiological Measures”).
3. Attentional Bias Task (ABT) – In a task adapted from Garner and colleagues (Garner et al. 2006) participants will be presented with pairs of faces, one on each side of a computer screen. Each pair will contain one neutral face and one 100% emotional expression taken using the same actor. The emotional expressions used will be from the standardized Karolinska set (Goeleven et al. 2008). Participants will be shown a central fixation cross for 1,000 ms, then the pairs of faces side by side for 500 ms. To distract participant attention from the primary purpose of the task, and reduce response bias, a probe (either an up arrow or a down arrow) will be presented in the same location as one of the previous pictures after each trial. Participants must respond to the direction the arrow is pointing by pressing a key. After a response, or after 10s have elapsed with no response, an intertrial interval of 750 to 1,250 ms will begin, followed by the presentation of another trial.
4. Interpersonal Speech Task (IST) – This is a controlled interaction task previously validated in our lab (Wardle et al. 2011) The IST is a semi-structured dialog task designed to model certain aspects of the psychotherapeutic encounter. During the IST, participants will be asked to describe a significant person in their life. They will be given 5 minutes to speak about this person with the research assistant, who will be trained in basic active listening skills (Sommers-Flanagan and Sommers-Flanagan 2009). Transcription and textual analysis by the Linguistic Word Count and Inquiry

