Program will be used to examine the total number of words as an index of social activity, and the amount of positivity and the amount of negativity expressed in each speech task, as a behavioral index of affect (Pennebaker et al. 2007).

Subjective Measures:

1. Profile of Mood States – POMS (McNair et al. 1971). The POMS is a validated measure consisting of 72 adjectives commonly used to describe momentary mood states. The POMS is highly sensitive to the effects of drugs in similar samples of healthy volunteers (de Wit & Griffiths, 1991; Johanson & Uhlenhuth, 1980), and will be used to assess mood effects of the drug during the study sessions.
2. Drug Effects Questionnaire – DEQ (Fischman and Foltin 1991). The DEQ is a validated measure consisting of questions on a visual analog scale about the subjective effects of drugs. Subjects are asked to rate the extent they feel a drug effect, whether they like or dislike the drug effect, and if given a choice would they want to take more of the drug. This is also be used to assess the pharmacodynamics of the drug effect during the study
3. The Addiction Centre Research Inventory – ARCI (Martin et al. 1971). The ARCI is a true-false questionnaire that consists of empirically derived scales sensitive to the effects of a variety of classes of psychoactive drugs (Haertzen 1966). We used a 53-item version, which yields scores for six scales that include: sedation (Pentobarbital-Chlorpromazine Group; PCAG), stimulant-like effects (Amphetamine; A, and Benzedrine Group; BG), somatic and dysphoric effects (Lysergic Acid; LSD), euphoria (Morphine-Benzedrine Group; MBG), and marijuana-like effects (M).
4. The Evaluative Space Grid – ESG (Larsen et al. 2009). The Evaluative Space Grid is validated measure consisting of a two dimensional grid that provides a single item measure of positivity and negativity. This will be used to measure subjective reactions to the IAPS pictures.

Psychophysiological Measures:

1. Cardiovascular measures – Blood pressure and heart rate will be periodically monitored using portable blood pressure cuffs, to track the cardiovascular effects of the drug, and ensure participant safety.

Procedure:

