Debriefing: Participants will return to the lab for a final session at which they will complete a final DEQ rating of how much they liked each study drug and how much they would want to take each study session drug again. Participants will also be asked to report which type or types of drugs they think they received at each session. Finally, participants will be fully debriefed with regard to the study hypotheses, methods and the types of drugs that they received, and will be given a chance to ask any final questions.

Data Analysis

IAPS: We hypothesize that participants will react less to negative pictures while taking CBD, while reactions to positive and neutral slides will be unchanged. We will conduct a Mixed Linear Model analysis in R using lme4 on each dependent variable (subjective ratings, corrugator and startle responses) using Drug (0, 300, 600 and 900mg) and picture type (positive, neutral, negative) as independent variables, and including random variables for Subject and Drug.

DEIT: We hypothesize that participants will show decreased sensitivity to negative facial expressions (anger, sadness and fear) on CBD, as measured by a greater intensity of expression required to identify negative facial expressions, but unchanged intensity for happy facial expressions. We also hypothesize that CBD will reduce negative psychophysiological responses to negative facial expressions, but not happiness. We will conduct a Mixed Linear Model analysis in R using lme4 on each dependent variable (expression intensity and corrugator responses) using Drug (0, 300, 600 and 900mg) and expression type (happy, angry, fearful, sad) as independent variables, and including random variables for Subject, Drug and Actor.

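### The IAPS corrugator model has no term for the 1 s pre-picture EMG baseline and the plan does not say how that baseline is used, so precision is lost and, if raw EMG is scored, some drug comparisons are open to a change in muscle tone

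*Combined protocol and SAP*

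**What the plan says.** Study Tasks, item 1 (IAPS), plans facial EMG "responses during a 1s baseline recording period will precede each picture, and during the 6s presentation of each", so a pre-stimulus value exists on every picture trial. It refers to Psychophysiological Measures for detail. In the text available, that section has a single entry, on cardiovascular measures ("Blood pressure and heart rate will be periodically monitored using portable blood pressure cuffs").

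The IAPS paragraph of Data Analysis gives the outcomes and fixed effects as "subjective ratings, corrugator and startle responses) using Drug (0, 300, 600 and 900mg) and picture type (positive, neutral, negative". The model also has random terms for Subject and for Drug. The hypothesis is selective: "participants will react less to negative pictures while taking CBD, while reactions to positive and neutral slides will be unchanged". That is a Drug by picture-type pattern, although the interaction is not written out as a model term. Neither section says how the baseline enters the corrugator score.

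The IST paragraph derives per-participant drug effects on responses to negative stimuli and enters them in the mediation model. For the DEIT, "EMG measurements will also be taken while participants view the facial expressions to examine psychophysiological reactions to the expressions", but no baseline window is named. Drug and Doses allows that "CBD alone may produce mild sedation".

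**The concern.** EMG level during a picture combines resting tone with the reaction to the picture. Tone can differ between sessions through electrode placement, and it can fall if CBD is mildly sedating. Aim 1 concerns the reaction, and the Significance section wants selective anxiolysis told apart from general sedation.

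If corrugator responses means raw level, a general fall in frown-muscle tone on CBD lowers the negative-picture value with no change in emotional reactivity. The same shift enters the per-participant estimates used for mediation. If it means change from baseline, the shift is subtracted out, but subtraction alone is not the most precise use of a noisy 1 s window. Leaving the scoring open also leaves an analyst's choice to be made after the data are in.

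**Working it through.** **Inputs.** From the documents: a 1 s baseline and a 6 s picture window, four drug levels, three picture types, and 36 expected completers. The documents give no significance level, power, effect size, EMG variance or baseline-picture correlation, so there is no planned figure to reproduce. Everything else below is assumed: two-sided 0.05, paired d = 0.4, equal baseline and picture variances, and a trial-level correlation ρ shown over a range.

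**Residual variance per trial, relative to raw level.** Raw = 1; change score = 2(1 − ρ); baseline as covariate = 1 − ρ².

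| ρ | Raw | Change | Covariate |
|---|---|---|---|
| 0.3 | 1 | 1.40 | 0.91 |
| 0.5 | 1 | 1.00 | 0.75 |
| 0.7 | 1 | 0.60 | 0.51 |
| 0.9 | 1 | 0.20 | 0.19 |

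Subtraction beats raw level only when ρ > 0.5. The covariate is never worse than either.

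**Power, covariate added to a change score.** The variance ratio is (1 − ρ²)/[2(1 − ρ)] = (1 + ρ)/2. If a share f of the contrast variance is trial noise, total variance is multiplied by 1 − f[1 − (1 + ρ)/2], and d becomes 0.4 divided by the square root of that factor. Without the covariate, the noncentrality is 0.4 × √36 = 2.4 on 35 df, giving power 0.646.

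| ρ | Factor, f = 1 | Power | Factor, f = 0.5 | Power |
|---|---|---|---|---|
| 0.5 | 0.75 | 0.769 | 0.875 | 0.704 |
| 0.7 | 0.85 | 0.716 | 0.925 | 0.680 |
| 0.8 | 0.90 | 0.691 | 0.95 | 0.668 |

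Against raw level the ratio is 1 − ρ². At ρ = 0.5 this is again 0.75, so power goes from 65% to 77%, 70% or 67% for f = 1, 0.5 or 0.25.

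**Bias from an additive tone shift δ.** With no true effect on reactivity:
- raw CBD-placebo difference within negative pictures = δ;
- change-score difference = δ − δ = 0;
- Drug by picture-type contrast, negative minus neutral = δ − δ = 0 under either scoring.

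Simulations assumed 36 subjects, 12 pictures per type, δ = −0.3 of the trial-level SD, and paired t-tests on subject means. In 400 runs at ρ = 0.7, the 900 mg versus placebo main effect was rejected in 95% of runs on raw level and 5% on change scores. The negative-minus-neutral contrast was rejected in 5% and 4%. In 1,000 runs of placebo against one dose, the estimate and rejection rate for negative pictures were:

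| Scoring | ρ = 0.5 | ρ = 0.7 |
|---|---|---|
| Raw level | −0.30, 84% | −0.30, 86% |
| Raw level with uncentred baseline as covariate | −0.15, 58% | −0.09, 39% |
| Change score plus session-centred baseline | 0.00, 6% | 0.00, 4% |

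The middle row shows why centring matters. The baseline is recorded after dosing, so CBD can change it, and an uncentred covariate removes only part of the shift.

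**Interaction power** with a true effect of −0.2 on negative pictures was 54% (raw), 50% (change) and 62% (change plus centred baseline) at ρ = 0.5, and 50%, 74% and 82% at ρ = 0.7. This simulation has no between-person variation in reactivity, so it sits at the favourable end (f = 1).

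**Limit.** An assumed 20% proportional fall in EMG amplitude does reach the interaction: 19% rejection on raw level and 28% on change scores. Subtraction does not remove it.

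**The case against.** The strongest reply is that a response measured beside a pre-picture baseline is naturally a baseline-corrected score, so nothing may be wrong beyond an undefined term. That reading is open. A reader might infer that the plan analyses raw EMG; no section says so. The EMG detail may also have stood in text not available here: the reference list contains a guideline on startle eyeblink EMG that the body never cites.

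A reader might also infer that a tone shift could produce the predicted selective effect. An additive shift cannot, because it lowers all picture types alike and cancels in the contrast that matches the hypothesis. The model is also more than Drug and picture type. If the random Drug term is by subject, it absorbs session-level tone differences between people, including electrode placement, though not a mean shift on CBD.

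Sedation is addressed elsewhere too. The Significance section treats dampened positive responses as its marker, and the exploratory mood analysis uses ARCI sedation as a covariate. Neither measures facial muscle tone.

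Finally, the gain is assumed and can be small. With half the variance at trial level and ρ = 0.7, it is 68.0 − 64.6 = 3.4 points against change scores, so a uniform gain of 5 points or more cannot be claimed.

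These points narrow the concern but do not remove it. No model has a baseline term, so precision is lost under either reading.

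**Conclusion.** The concern holds in a limited form. The corrugator response is undefined in the available text, and a baseline already collected on every picture trial is absent from the model.

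On raw scoring, an additive tone change biases the Drug main effect, the comparison within negative pictures and the estimates sent to the mediation analysis. On change scores these are protected. In the Drug by picture-type contrast, an additive shift causes no bias under either scoring and the loss is precision: about 4 to 12 power points against change scores if all contrast variance is trial noise, and 2 to 6 if half is, over ρ from 0.8 down to 0.5.

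These figures rest on d = 0.4, n = 36, two-sided 0.05 and equal variances. The documents supply only the 36. The documents do not support a conclusion that the planned test of selectivity is invalid.

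**What to change.** In the IAPS paragraph of Data Analysis:

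1. Define the corrugator outcome as mean EMG over the 6 s picture minus mean EMG over that trial's 1 s baseline, and state any transformation.
2. Add the trial baseline, centred on its session mean, as a covariate. Subtraction removes a session-level shift and the covariate recovers trial-level precision. Because the centred term averages to zero within a session, it sharpens picture-type contrasts but not the Drug main effect.
3. Write the Drug by picture-type interaction as the test of the hypothesis.
4. Report the Drug effect on baseline EMG. A clear effect warns of a tone or amplitude change, including a proportional one that subtraction leaves in place.
5. State the picture order. The covariate is safe for the interaction if picture type cannot affect the following baseline, which needs unblocked presentation or no carryover.

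For the DEIT corrugator outcome, use the same approach only if the opening neutral frames last long enough to give a usable baseline; the documents give no frame timing.

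The cost is a few sentences of analysis text and one extra slope, with no new data. The gain is small if ρ is very high and change scores would have been used anyway, or if trial noise is a small share of the variance.

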Detailed Protocol

Title: Effects of cannabidiol on responses to emotional stimuli (“Effects of drugs on mood and behavior” on the consent form)

P.I.: [name]

Co-Investigators: [name], [name], [name]

May 11, 2016

Objectives: To study the effects of cannabidiol (CBD), a constituent of marijuana, on responses to emotional stimuli in healthy young adults.

Aim 1. We will assess the effects of CBD on subjective and psychophysiological responses to images with positive (rewarding) vs. negative (aversive) emotional content. Our working hypothesis is that CBD will reduce subjective and psychophysiological responses to negative images without affecting responses to positive images.

Aim 2. We will examine the effect of CBD on responses to the socially rewarding and aversive information conveyed by emotional facial expressions. We will measure speed of identification for positive (rewarding) and negative (aversive) emotional expressions as they dynamically develop, psychophysiological reactions to emotional expressions and direction of attention to emotional expressions. Our working hypothesis is that CBD will slow identification of negative expressions, reduce psychophysiological responses to negative expressions, and reduce direction of attention to negative expressions without affecting responses to positive expressions.

Aim 3. We will examine the effect of cannabidiol on a controlled social interaction with a research assistant. Our working hypothesis is that the reduction in responses to negative emotional and social stimuli produced by CBD will result in greater talkativeness in a controlled social interaction.

Exploratory Aim. We will additionally measure the effects of CBD on subjective mood, including anxiety, euphoria and sedation, to determine whether the CBD’s effects on responses to emotional stimuli are mediated by effects on subjective mood, or occur above and beyond CBD-induced changes in mood.

Significance

The purpose of this project is to investigate the effects of cannabidiol (CBD) on responses to emotional stimuli in humans. CBD is one of the primary constituents in whole plant marijuana (Ashton 2001). Such cannabinoid compounds are of interest for two reasons. First, understanding the effects of these compounds may shed light on the phenomena of marijuana use and abuse. Second, studying the effects of cannabinoids may be informative about the purposes and functioning of the brain’s endocannabinoid

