In a four-session within-subjects study we will compare a placebo control to 300, 600 and 900mg of cannabidiol. In Aim 1 we will explore how cannabidiol affects reactions to rewarding vs. aversive pictures. Participants will view pleasant pictures (e.g. of parties, pets, sunsets), neutral pictures (e.g. of household objects, neutral landscapes) and unpleasant pictures (e.g. medical imagery, war scenes and disgusting objects) drawn from the standardized International Affective Picture Set (IAPS) while we measure subjective responses to these pictures using self-reports. We predict that cannabidiol will reduce subjective and psychophysiological responses to negative pictures without affecting responses to positive pictures. In Aim 2 we will examine responses to emotional facial expressions, which are an ecologically relevant category of rewarding and aversive stimuli. We will measure how quickly individuals are able to perceive happy vs. negative facial expressions using dynamically developing expressions of happiness, fear, anger and sadness. We predict that cannabidiol will blunt perception of, psychophysiological responses to and attentional bias towards negative facial expressions without affecting responses to positive facial expressions. In Aim 3 we will examine the relationship of responses to emotional stimuli with talkativeness in a controlled social interaction. We predict that cannabidiol will increase talkativeness, and this effect will be mediated by the decreased responses to negative social and emotional stimuli measured in the previous aims. Finally, on an exploratory basis we will measure the subjective effects of cannabidiol, and specifically the its effects on anxiety, sedation and euphoria, with the aim of determining whether CBD's effects on responses to emotional stimuli are related to, or independent of, its subjective effects.

Methods:

Design: The study will use a 4-session within-subjects double-blind design in which participants will receive three doses (300, 600mg and 900mg oral) of cannabidiol and a placebo in randomized order. All screening, orientation, and study session procedures

will take place in the Human Behavioral Pharmacology Laboratory suite in the L4 wing of [name]

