ABT: We hypothesize that participants will show reduced attentional bias to negative facial expressions (anger, sadness and fear) on CBD, as measured by increased reaction times for probe response for negative faces, without any change in responses to happy faces. We will conduct a Generalized Mixed Linear Model analysis in R using lme4 on the binomial variable of initial gaze direction with Drug (0, 300, 600 and 900mg) and expression type (happy, angry, fearful, sad) as independent variables, and including random variables for Subject and Drug. We will conduct a Mixed Linear Model analysis in R using lme4 on total dwell time on each face, using Drug (0, 300, 600 and 900mg) and expression type (happy, angry, fearful, sad) as independent variables, and including random variables for Subject and Drug.

IST: We hypothesize that participants will show increased talkativeness on the IST, as measured by total word count and further, that this increased talkativeness will be mediated by reduced negative responses to negative emotional and social cues (as measured in the IAPS, DEIT and ABT). We will first derive per-participant estimates of the effect of drug on responses to negative stimuli from the Mixed Linear Model analyses described above. We will then conduct a Mixed Linear Model analysis in R using lme4 on total word count with Drug (0, 300, 600 and 900mg) as an independent variable, and including random variables for Subject and Drug (per Wardle et al. 2012b). Following criteria for within-subject mediation (Judd et al. 2001), we will first establish whether drug has the hypothesized effect on talkativeness. We will then include the per-participant estimates of the effect of drug on responses to negative stimuli as covariates, and examine 1. Whether changes in responses to negative stimuli account for a significant proportion of changes in talkativeness, and 2. Whether the effect of drug on talkativeness is still significant after inclusion of the changes in responses to negative stimuli. If the effect of drug on effort is wholly mediated by changes in responses to negative stimuli, we would expect the effect of drug on talkativeness to no longer be

significant after including drug-induced changes in responses to negative stimuli as a covariate (see Wardle and de Wit 2012 for an example of this type of analysis).

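### The attentional-bias prediction is worded on probe reaction time, but the only planned ABT models are for gaze direction and dwell time

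*Combined protocol and SAP*

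**What the plan says.** Objectives, Aim 2, predicts that CBD will "reduce direction of attention to negative expressions without affecting responses to positive expressions". The aims summary in Significance likewise expects blunting of "attentional bias towards negative facial expressions without affecting responses to positive facial expressions". Neither statement says how attention is to be measured.

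Data Analysis, ABT paragraph, supplies the measure: bias to angry, sad and fearful faces is expected to fall "as measured by increased reaction times for probe response for negative faces", with happy faces unaffected. Two models follow. The first reads "We will conduct a Generalized Mixed Linear Model analysis in R using lme4 on the binomial variable of initial gaze direction". The second is a linear mixed model on "total dwell time on each face, using Drug (0, 300, 600 and 900mg) and expression type (happy, angry, fearful, sad) as independent variables". Both have Drug and expression type as independent variables and random terms for Subject and Drug.

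Study Tasks item 3 describes the task. Each trial shows a pair of faces of one actor, one neutral and one emotional, for 500 ms. An arrow then appears where one of the faces had been, and the participant presses a key for its direction. The stated reason for the arrow is: "To distract participant attention from the primary purpose of the task, and reduce response bias, a probe" is shown.

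**The concern.** The measure that would confirm or refute the ABT prediction is not among the measures to be analysed. A gaze or dwell result would bear on the general Aim 2 statement but would leave the written reaction-time prediction untested. The task description adds to the conflict, because it treats the probe as a device to occupy the participant rather than as the outcome.

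With one measure in the hypothesis and two in the models, and none named as primary, a later reader could not tell which result was meant to count. The choice could then be made after the data are seen.

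**Working it through.** The plan gives no effect size, variance, alpha or power figure for the ABT, so there is no figure to reproduce. The check is a comparison of texts.

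**Step 1. Prediction against model, task by task (Data Analysis).**

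| Task | Measure in the prediction | Measures modelled | Match |
|---|---|---|---|
| IAPS | smaller reactions to negative pictures, no single measure named | subjective ratings, corrugator, startle | yes, at the level of the construct |
| DEIT | intensity needed to identify the expression; negative psychophysiological response | expression intensity; corrugator | yes |
| ABT | probe reaction time | initial gaze direction; total dwell time | none |
| IST | total word count | total word count | yes |

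Only the ABT names a specific measure and then models others. Predicted: 1. Modelled: 2. Overlap: 0.

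**Step 2. Is reaction time analysed elsewhere?** The IST mediation reuses the models already described, and the exploratory mood analysis refers only to responses to negative stimuli. Neither adds a reaction-time model.

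**Step 3. Which outcome was meant?** Four things favour gaze: both models; the distractor role of the probe; the Aim 2 wording about direction of attention; and the study from which the task is adapted, whose title in References concerns gaze to facial expressions. Two things favour reaction time: the hypothesis clause itself, and the fact that the key press is the only ABT response described. The balance is toward gaze, without proof.

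**Step 4. Is gaze recorded?** The Psychophysiological Measures list holds only blood pressure and heart rate. However, the IAPS and DEIT task descriptions refer to that section for EMG, and Data Analysis models corrugator and startle, none of which is listed. The list is incomplete for measures that the plan plainly intends, so its silence on gaze settles nothing.

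**Step 5. Would changing only the outcome in the existing models be enough if reaction time is chosen?** This bears on the fix, not on the finding. Let bias be reaction time with the probe at the neutral face minus reaction time with the probe at the emotional face. Suppose CBD lowers bias to negative faces by b, of which a share p appears at the negative face, leaves bias to happy faces unchanged, and slows all responses by g. The changes on CBD are:
- probe at negative face: g + p·b
- probe at its neutral partner: g − (1 − p)·b
- mean of the two locations at 50:50: g + (p − 1/2)·b
- location difference (neutral minus negative): −b, whatever g and p are
- either location in happy pairs: g

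With assumed values b = 20 ms, p = 1/2 and g = 20 ms, the negative-face change is 20 + 10 = 30 ms and the happy-face change is 20 ms. The difference between expressions is 30 − 20 = +10 ms, and the location difference is −20 ms. With g from 10 to 40 ms, the negative-face change runs from 20 to 50 ms, while the last two figures stay the same. With p from 0 to 1, the between-expression difference at the emotional face runs from 0 to 20 ms, and the same difference pooled over locations runs from −10 to +10 ms. Only the location contrast recovers b throughout. None of these inputs comes from the trial.

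**The case against.** The strongest reply is that this is one mis-worded clause. The construct is reduced attentional bias, two planned analyses address it, and Step 3 shows where the intention lies. Most of that stands, and it limits the point to the prediction as written. It does not remove it: the clause is the only place where the ABT measure is tied to a direction of effect.

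A reader might infer more than the documents support:

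- *That the Aim 2 attention hypothesis has no analysis.* Initial gaze direction addresses it if coded toward versus away from the emotional face. That coding is not stated, but it is the natural one for these pairs.
- *That gaze is not recorded, so neither model can be run.* This rests on silence in a list that also omits EMG. The reference list also carries a startle-EMG guideline that the body text does not cite, so text on measures may have been cut.
- *That the dwell model cannot detect a shift between the two faces.* The shift cancels only if both faces of a pair are entered under the pair's expression, so that a neutral face is labelled with an emotion. Expression type has four emotional levels and no neutral level, which makes that reading unlikely.
- *That general slowing would defeat any reaction-time analysis.* Drug and Doses allows for mild sedation, but slowing that is equal across expressions drops out of the Drug-by-expression interaction, as Step 5 shows. It affects the simple prediction of a rise at negative faces and no change at happy ones.
- *That the mismatch specifically undermines Aim 3.* The IST mediation takes "estimates of the effect of drug on responses to negative stimuli from the Mixed Linear Model analyses described above" without naming the measure, but responses are to be taken "as measured in the IAPS, DEIT and ABT", and the IAPS and DEIT also have several outcomes each. The unnamed mediator is a separate, general matter.

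**Conclusion.** The point holds in its narrow form. The ABT prediction is stated on probe reaction time, no reaction-time analysis is planned, and the task description gives the probe a different purpose. This follows from the text alone and needs no assumption.

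Its reach is one of the two facial-expression tasks under Aim 2. Gaze is the more likely intended outcome, and the planned gaze models can inform the broader question. Whether gaze data exist cannot be determined from the supplied text. The millisecond values in Step 5 are illustrations that explain the probe-location term, and the finding does not rest on them. It should be fixed before analysis, but it does not put the trial's design in doubt.

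**What to change.** Before ABT data are seen, confirm what the ABT records, name the primary ABT outcome, and make hypothesis and model agree.

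- **If gaze is recorded:** describe the recording. Restate the hypothesis as a lower probability on CBD of first gaze toward, rather than away from, the negative face. Make dwell on the emotional face relative to the neutral face of the same pair the secondary measure. Test each by the Drug-by-expression interaction, written out explicitly.
- **If reaction time is the outcome:** add a reaction-time model with Drug, expression type and probe location (emotional versus neutral face), including their interactions. A rise at the negative face alone does not separate reduced bias from general slowing. Correct the statement of the probe's purpose in Study Tasks item 3, and remove the gaze and dwell models if no gaze data exist.

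The cost is wording, or one additional model on key-press responses that the task already collects, with no extra participants. If gaze is wanted but proves not to be recorded, recording would have to be added to the task; the documents do not show whether that case applies.
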